#### Specific aims

1. Demonstrate the feasibility of implementing PiPT in a US Navy shore-based health care setting. We will analyze SOAP notes to assess whether the clinicians have applied aspects of the training in the treatment given to the patients and they are reflected in the notes.
2. Document and compare baseline risk factors related to pain interference in two cohorts of patients with MSD.
3. Demonstrate the effectiveness of a PiPT intervention on psychological and functional work outcomes in a comparative effectiveness trial through a relative increase in protective follow-up measures such as quality of life, self-efficacy, and satisfaction and a relative decrease in detrimental measures like pain catastrophizing, fear of movement, and distress.

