###### Treatment

- After signing the consent form, the participant will complete a paper form collecting contact information for follow-up and demographic information. At this point, the participant will be assigned a participant ID number. The researcher will verify the participant's diagnostic code and therapist using AHLTA afterward.
- Before the participant's next PT appointment, the participant will complete the baseline questionnaire battery, a 139 question survey battery. The participant may complete the battery immediately on paper, or at a later date online using a link to REDCap that will be sent via encrypted email. This battery must be completed before their next appointment.
- Participants will receive standard PT care as prescribed and scheduled by their therapist. Participation in the study will not alter their care plan.
- Participants will complete follow up questionnaire batteries after their 4th PT appointment\*, 6mo and 12mo post enrollment. The first follow-up questionnaire is a 77 question survey battery. The second and third follow-up points use a 68 question battery. All follow-up questionnaires will be completed remotely via REDCap.
- We will collect de-identified SOAP notes from randomly selected participants and review them for verbiage indicating that the therapist employed principles of PiPT. We will collect up to 30 SOAP notes, pertaining to various physical therapists and throughout various stages of treatment.

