#### **Questionnaires/Outcomes**

The self-report questionnaire batteries are largely composed of the validated survey tools and single-item questions.

1. The Pain Disability Index (PDI) will measure pain interference.
2. Catastrophizing will be assessed by the Pain Catastrophizing Scale (PCS).
3. Fear avoidance beliefs will be assessed using the Fear Avoidance Beliefs Questionnaire (FABQ). (Excluding "I have a claim for compensation for my pain," no relevance).
4. Psychological distress will be measured using the Hospital Anxiety and Depression Scale (HADS).
5. Self-efficacy will be assessed using the Pain Self-Efficacy Questionnaire (PSEQ).
6. *Positive outcome expectations* will be assessed using a 5 point single item scale developed for the military population by Stephanie Booth-Kewley et al. (2009).

7. Satisfaction with process of care will be measured by the "process of care" subscale of The MedRisk Instrument for Measuring Patient Satisfaction (MRPS).
8. Outcome satisfaction (single item scale): 'If you had to spend the rest of your life with the symptoms you have right now, how would you feel about it? This is derived from the Core Outcome Measures Index (COMI) questionnaire.
9. Clinical Depression: The Center for Epidemiologic Studies Depression Scale (CES-D).
10. Anxiety Disorder: General Anxiety Disorder Screener (GAD-7).
11. Post-Traumatic Stress Disorder (PTSD) will be assessed using the PTSD Checklist – Military version (PCL-M).
12. Job satisfaction (single item scale): "Taking everything into consideration, how do you feel about your job as a whole?" taken from Dolbier et al. (2005).
13. Work stress (single item scale): "Taking everything into consideration, how stressful is your job as a whole?"
14. Organizational commitment (single item scale): Commitment will be assessed by the affective dimension of the Commitment Scale.
15. Job social support: Subject's relationships with co-workers and social environment at their job, drawn from the Deployment Risk and Resilience Inventory-2 (DRRI) unit support subscale.

Injury history: affected body part(terminology adopted from Barrel matrix.), time since onset, other MSD comorbidities, episode recurrence, previous MSD and pain intensity.

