#### Baseline Questionnaire Battery

- 139 questions charted below and one open field question on any barriers to treatment the participant perceives.

C  
 o V  
 V I I a R C  
 A e rie i  
 A c a s t  
 R T b p a  
 I O l o a  
 A O t  
 A n e n i  
 B L T s o  
 L o y e n  
 E i p s n  
 n e  
 t  
 B  
 T a  
 T s C S  
 o T e h o el  
 b li n e  
 a r foctn  
 c e u fr/  
 c e n o a  
 o It u d m  
 U r e e Li  
 s v m r st  
 e e  
 y  
 B  
 a D  
 s e S  
 E e Simel  
 d li n o e  
 u n g l g c t n  
 c e e r fr/  
 a S I t a o a  
 t i ue p m  
 o r m h i L i  
 n v c st  
 e s  
 y  
 B  
 a  
 s

e  
P li  
ri n  
m e  
a S D  
r u e S  
y r Simel  
I v n o e  
nj eglg ct  
u y e r fr8  
r , Ita o 5  
y F e p m  
L o mhiLi  
o ll c st  
c o s  
a w  
ti \_  
o U  
n p  
1  
,2  
,3

>  
4  
w  
e  
e  
k

B s,  
Tia D 4  
ms e -  
e e Sim 1  
si li n o 2  
n nglg n  
c e e r w /  
e S Ita e  
o u e p e  
n r mhi  
s v c s,  
ete s <  
y 1  
2  
w  
e  
e  
k  
s

E  
piB  
s a D  
o s e  
d e Sim Y  
e li n o e  
R nglg s n  
e e e r / /  
c S Ita N a  
u u e p N  
rrr mhi o  
e v c  
n e s  
c y  
e  
B  
p a D  
r s T e Y  
e e m e  
e li w o

vin o g s n  
o e Itr / /  
u Se a Na  
s u m p o  
Mr hi  
S v c  
De s  
y  
B  
a  
s  
e  
li  
n  
e  
S  
u D  
P r e 0  
aiv Sim 0  
n en o 1  
in y glg 0 n  
t , e r S /  
e F Ita a  
n o e p c  
n o e p al  
sill mhi e  
tyo c  
w s  
-  
U  
p  
1  
,,  
2  
,,  
3  
B  
M a D  
S s e S  
D e Simel  
c lin o e  
o n glg ct 8  
- e e r fr 5  
m S Ita o  
o ue p m  
r r mhi Li  
bi v c st  
di e s  
ty y  
B  
a  
s  
e  
li I  
On n  
u e d  
tcS e  
o u p  
mr Sie 0  
e v n n -  
e e gld 5  
x y e e s 1  
p , it n c 7  
e F e t al  
cto m V e  
a ll a  
ti o ri  
o w a  
n - bl  
e

U  
p  
1  
B  
a  
s  
e  
li  
n  
e D  
S e  
u p  
r e  
Q v Sin 5  
u end p  
al ygle t n  
It , e n s /  
y F Itt c a  
of o e V al  
Li ll ma e  
fe o ri  
w a  
- bl  
U e  
p  
1  
,, 2  
,, 3  
B  
a  
s  
e  
li  
n 0  
p e D -  
S e 1  
ai u p 0  
n r e s  
I v n c  
n e d al  
t y P e e 6  
e y P e e 6  
rf , D n ; 0  
FI t 7  
e o V q  
r ll a u  
e o rie  
n w a st  
c - blio  
e U e n  
p s  
1  
,, 2  
,, 3  
B  
a  
s  
e  
li  
n  
e 0  
S D -  
u e 6  
r p s  
S v e c  
el n  
f d

efe P e al6  
fi y S n e7  
c , E t ;  
a F Q V 1  
c o a 0  
y ll ri q  
o a u  
w ble  
- e st  
U io  
p n  
1 s  
,

2

,

3

B

a

s

e

li

n 0

P e D -

ai S e 4

n u p s

Cr e c

a v n al

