
t e d e

a y P e ;6

st, C n 11

r F S t 31

o o V q

p ll a u

hio rie

zi w a st

n - blio

g U e n

p s

1

,

2

,

3

B

a

s

e

li

n 0

e D -

F S e 6

e u p s

a r e c

r v n al

ofe d e

my F e ;6

o , A n 12

v B t 52

e o Q V q

mll a u

e o rie

n w a st

t - blio

U e n

p s

1

,

2

,

3

B  
a  
s  
e  
li  
n 4  
e Dp  
S et  
u ps  
r ec  
D v nal  
is e de  
tr y A n 6  
e ' D t 4  
s S Vq  
s o ll a u  
o rie  
w a st  
- blio  
U en  
p s  
1

,

2

,

3

A

ff 5

e p

O Bct t  
r aiv Li  
g s e C k  
g e co e  
c li o n e  
o n mfo rt  
m e mu ; 8  
m S it n 4 0  
it u md q  
m r e e u  
e v n r e  
n v n r st  
t et io  
t y s n  
c n  
al s  
e

5

p

J B t  
o a Li  
b s C k  
s e o e  
o li n rt  
cin D fo; 8  
cin R u 1 4  
s S R n 2 4  
u u d q  
p r e u  
p v r e  
o e st  
rty io

n

s

1

-

5

B s  
a c  
s C  
e o

li P n al  
n Cfoe 7  
eL u ; 7  
S- n 1  
uMd 7  
r eq  
v ru  
e e  
y st  
io  
n  
s  
0  
-

B 3  
a s  
Ds Cc  
e e o al  
p li Cn e  
r nE fo; 7  
e eSu 2 4  
s S- n 0  
siuDd q  
o r e u  
n v r e  
e st  
y io  
n  
s  
0

B -  
a 3  
s C s  
e o al  
A li Gn e  
n nA fo; 7  
xieDu ; 7 6  
e S- n  
tyu 7 d q  
r e e  
v r st  
e io  
y n  
s

B  
a  
s  
e  
li  
n  
e  
M S  
e u  
n r C  
t v h o Y  
al e h n Y  
H r fo e n  
e e e s n  
al' e u / /  
t F n a  
t o d N  
h ll e o  
C o m r  
a w  
r -  
e u  
p  
1  
,

,  
3  
B  
J a  
o s C  
b e Sio 1  
s l i n n -  
a n g l f o 5 7  
t i e e u s 9  
s f S i t n c  
a u e d a l  
c t r m e e  
i o v r  
n e

y  
B  
a  
W s C  
o e Sio 1  
r l i n n -  
k n g l f o 5 n  
s t e e u s /  
r S i t n c a  
e u e d a l  
s r m e e  
s v r  
e  
y

F  
u l  
B I  
a D  
s u  
e t  
l i y  
n ;  
e Li  
S m  
u it  
Dr e  
u v Sio d  
t y e n n D  
S y g l f o t n  
t , e u y /  
a F i t n a  
t o e d ;  
u l l m e M  
s o r e  
w d  
- B  
u o  
p a  
1 r  
, ;  
2 O  
, t  
3 h  
e  
r

P  
e  
rc D  
e i B e F  
v a p r  
e s e e  
d e S i n e  
b l i n d R  
a n g l e R  
r r e e n e

ieSItt s 1  
rsue V p 1  
r ma o  
t v rin  
o e as  
c y ble  
a e  
r  
e

Follow-up Questionnaire Batteries

- Post 4th treatment session- 77 items long, including one open field question
- 6 and 12mo – 68 items (excludes MRPS scale and outcome expectation)

C  
o V  
II a R C  
A e rie i  
R c ass i  
T ti b p t  
I O l o a  
A O l o t  
B L en i  
P T s o  
L o y e n  
E i p s n  
n e  

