## 11.6 Data Analysis Plan: Complete description: Background, Objectives, Design, Step by Step how the project is going to be done, Data analysis plan:

In order to assess for significant differences between two cohorts of patients, bivariate comparisons will first be conducted using a Chi-squared (Fisher exact) test to compare proportions of categorical (dichotomous outcomes) and an unpaired t-test for mean changes of continuous outcomes (i.e. Pain Disability Index scale, self-efficacy, positive outcome expectation, catastrophizing, fear avoidance beliefs and distress).

Alternatively, Wilcoxon nonparametric counterpart will be used for continuous variables where there is deviation from normality. These univariate analyses will be followed by multivariable regression methods for an adjustment of all other potential confounding variables. We will also use longitudinal logistic models (i.e., mixed-effects regression models with a random subject effect and GEE with exchangeable and independent correlations) to analyze the changes of the outcome at baseline at all follow-up times (baseline, post-treatment, at 6 months, and 1 year). Psychological outcomes will be analyzed at baseline and at post-treatment (approximately 4 weeks of enrollment). The models will be specified with random intercepts and slopes such that a linear trajectory representing outcomes will be compared between two arms. For example, longitudinal changes in all available continuous psychological outcomes over time of follow-up will be displayed using locally weighted smoothing scatter (lowess) plots, identifying nonparametric mean trajectories over time. Mean trajectories then will be modeled with mixed-effects linear regression models, and if necessary using segment-linear models to approximate non-linear mean trajectories for ease of interpretation. Group (arm)-specific (as well as individual-level) intercepts and slopes over the period of follow-up will be included as random effects, while other covariates such as other clinical or demographic confounders will be modeled as fixed effects. An interaction term will be also assessed to test group differences in outcomes over time. Residual-based diagnostics will be used to evaluate validity of model assumptions. Two sided p-values <0.05 will be considered to be statistically significant. All statistical procedures will be performed using R statistical package ([www.R-project.org](http://www.R-project.org)).

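### The COMI symptom-satisfaction item is not asked at baseline, so the sequential-cohort comparison of this Aim 3 measure cannot be adjusted for its starting value

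*Combined protocol and SAP*

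**What the plan says.** Aim 3 (section 9.3) seeks to show effectiveness through a "relative increase in protective follow-up measures such as quality of life, self-efficacy, and satisfaction", alongside a relative decrease in detrimental measures. It does not say which satisfaction measure is meant.

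Section 10.2 lists two candidates:

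- **MRPS process-of-care subscale** (item 7). It concerns care received and is charted at follow-up 1 only.
- **Outcome satisfaction** (item 8), one question derived from the COMI: "If you had to spend the rest of your life with the symptoms you have right now, how would you feel about it". It is charted as a dependent variable at follow-ups 1, 2 and 3.

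The baseline chart has no outcome-satisfaction row; its only satisfaction row is job satisfaction. Quality of life and self-efficacy are charted at baseline and at every follow-up.

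For analysis, section 11.6 starts with "an unpaired t-test for mean changes of continuous outcomes", naming pain disability, self-efficacy, outcome expectation, catastrophizing, fear avoidance and distress. Multivariable regression and longitudinal models with baseline as the first time point follow. Satisfaction is not in the list of change outcomes, and no other analysis is given for it.

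**The concern.** The cohorts are not randomised and are enrolled one after the other, before and after the therapists are trained. They may differ at the start in how patients feel about their symptoms. The most direct control for that is each patient's own starting answer, and for this item it is not collected.

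The item asks about symptoms at the moment of asking, so nothing prevents its use before treatment. Follow-up 1 cannot serve as the starting value: section 10.1 says the investigators already expect the groups to differ by the fourth visit. Once a participant has begun treatment, the baseline answer cannot be recovered.

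At stake is one secondary-type measure. A difference present before treatment could be reported as a benefit of PiPT on satisfaction.

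**Working it through.** **1. Does the item count fit the schedule?** The charts are broken in the text, so I rebuilt the batteries from the legible item counts.

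*Baseline:* tobacco 3, education 1, injury location 1, time since onset 1, recurrence 1, previous MSD 2, pain 1, comorbidity 1, outcome expectation 1, quality of life 1, PDI 7, PSEQ 10, PCS 13, FABQ 15, HADS 14, organizational commitment 4, social support 12, PCL-M 17, CES-D 20, GAD-7 7, mental health care 3, job satisfaction 1, work stress 1, duty status 1, barriers 1. Sum = 139, with no COMI item.

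*Follow-up 1:* location 1, pain 1, outcome expectation 1, quality of life 1, PDI 7, PSEQ 10, PCS 13, FABQ 15, HADS 14, mental health care 3, MRPS 8, COMI 1, duty status 1, lessons learned 1. Sum = 77.

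*6 and 12 months:* 77 − 8 (MRPS) − 1 (outcome expectation) = 68.

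The plan gives the same sizes: "139 questions charted below and one open field question on any barriers to treatment the participant perceives"; "The first follow-up questionnaire is a 77 question survey battery"; and "68 items (excludes MRPS scale and outcome expectation".

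**2. The plan's own power figure.** Table 2 gives 84.9% for a standardised difference of 0.3 with 286 enrolled per cohort and 30% loss. Completers: 286 × 0.70 ≈ 200 per cohort. With SE = √(2/200) = 0.10 SD, the expected z is 0.3/0.10 = 3.0, and power = Φ(3.0 − 1.96) = 85.1% (84.9% with the noncentral t). The figure reproduces. It does not use baseline values, so the missing item leaves it unchanged.

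**3. Size of the exposure.** The documents give neither the baseline-to-follow-up correlation ρ of this item nor the gap between cohorts at the start; both are assumed. For a comparison at follow-up with no adjustment,

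bias = ρ × starting gap (SD units).

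| ρ | gap 0.1 | gap 0.2 | gap 0.3 |
|---|---|---|---|
| 0.4 | 0.04 | 0.08 | 0.12 |
| 0.5 | 0.05 | 0.10 | 0.15 |
| 0.6 | 0.06 | 0.12 | 0.18 |

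Against the plan's generic effect size of 0.3, the ends of the range are 0.04/0.3 = 13% and 0.18/0.3 = 60%.

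With no true effect and 200 per cohort, the bias shifts z by bias/0.10. At ρ = 0.5 the nominal 5% error becomes 7.9%, 17.0% and 32.3% for gaps of 0.1, 0.2 and 0.3. For example, at gap 0.2 the shift is 1.0, and 1 − Φ(0.96) + Φ(−2.96) = 17.0%.

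**4. What a baseline value would add.** As a covariate it reduces the outcome variance by ρ², that is 16% to 36% for ρ of 0.4 to 0.6. At ρ = 0.5 the residual SD is √(1 − 0.25) = 0.866, and power for 0.3 is Φ(0.3/(0.866 × 0.10) − 1.96) = 93.4%, against 85.1% for follow-up alone. A change score has SD √(2(1 − ρ)) = 1.0 at ρ = 0.5, so its power stays at 85.1%. This favours using the baseline as a covariate.

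**The case against.** Four points can fairly be made for the plan.

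- *The aim can be read as a comparison at follow-up.* It speaks of a relative increase in follow-up measures, which may mean one cohort against the other. That difference can be computed. This stands, but the comparison still carries any starting difference between the cohorts.
- *Confounding is partly addressed.* Section 11.6 plans multivariable adjustment, and baseline PDI, pain intensity and quality of life are collected. This also stands. The biases above are for an unadjusted comparison, and the proxies would remove some part that cannot be quantified from the documents. They do not replace the item's own starting value.
- *The size is assumed.* The upper end needs the largest correlation and the largest gap together, with no covariates, and 0.3 SD was not set for satisfaction in particular. This is correct.
- *The item count is supportive, not conclusive.* The baseline total reaches 139 only if the open barriers question is counted. If it is separate, the other charted items sum to 138 and one is unaccounted for. The follow-up total of 77 does include its open question, and no charted baseline row holds the COMI item.

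Two stronger readings are tempting. A reader might infer that no change at all can be computed; but change from follow-up 1 to 6 and 12 months can be. A reader might also infer that section 11.6 orders a change test that is impossible for this item; but satisfaction is not in its list of change outcomes. What the section lacks is any stated analysis for satisfaction.

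**Conclusion.** The point holds for the COMI item alone. It is an Aim 3 type of measure that could have a baseline value and is not charted with one. Change from baseline is unavailable, and the comparison of sequential cohorts cannot be adjusted for the item's starting level.

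Under the assumed correlation of 0.4 to 0.6 and starting gap of 0.1 to 0.3 SD, the bias before any proxy adjustment is 0.04 to 0.18 SD. This is an illustration, not an estimate of the error the final analysis would make. It also assumes a linear relation with equal spread in both cohorts. The planned sample size, the stated power and the other named Aim 3 measures are untouched. This is a cheap improvement and not a flaw that undermines the study.

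**What to change.** 1. Add the single COMI item to the baseline battery in both phases (139 to 140 items) and chart it in section 10.2. Adding it in Phase II alone would not permit the adjustment.
2. In section 11.6, state that the item at follow-ups 1 to 3 is compared between cohorts with its baseline value as a covariate, alongside the other planned confounders.
3. In the same section, state that MRPS process-of-care satisfaction is compared between cohorts as a follow-up 1 score. In Aim 3, say which satisfaction measure is meant and word the MRPS claim as higher, not increased.
4. If Phase I has already enrolled without the item, limit the COMI claim to a between-cohort difference at follow-up adjusted for baseline PDI, pain intensity and quality of life, and do not describe it as an increase from baseline.

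The cost is one extra baseline question and a minor instrument amendment. The fallback in step 4 needs only changes of wording.

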#### 9.4 Study Design:

Describe study design in one to two sentences (e.g., prospective, use of existing records/data /specimens, observational, cross-sectional, interventional, randomized, placebo-controlled, cohort, etc.). Specify the phase – Phase I, II, III, or IV – for FDA-regulated investigational drug research

We are proposing an observational prospective comparative cohort study. This study meets the criteria for a hybrid type 3 study; a hybrid type 3 study tests an implementation/strategy while observing/gathering information on the clinical intervention and related outcomes.

#### 9.5 Target Population:

Describe the population to whom the study findings will be generalized

Active duty service members receiving physical therapy for musculoskeletal disorders.

#### 9.6 Benefit to the DoD:

State how this study will impact or be of benefit to the Department of Defense

This study will demonstrate the feasibility and efficacy of implementing PiPT training at a military treatment facility in improving outcomes of musculoskeletal disorders. The ultimate goal is to decrease MSD-related chronicity leading to separation and disability in ADSM in support of combat readiness.

## 10.0

### Study Procedures, Data Management, and Privacy

#### 10.1 Study Procedures:

Describe step-by-step how the study will be conducted from beginning to end

##### Phase I

###### Recruitment and Consenting

- Research staff will review the PT clinic's schedule for patients scheduled for initial evaluation, then request an introduction from the therapist if appropriate (patient must be scheduled for at least 4 physical therapy sessions).
- Research staff will brief the patient on the study.
- If the patient is interested, the researcher will show them to the private study room, screen them for eligibility, and then ask them to review the consent form. The researcher will remain in the room to answer any questions.

###### Treatment

- After signing the consent form, the participant will complete a paper form collecting contact information for follow-up and demographic information. At this point, the participant will be assigned a participant ID number. The researcher will verify the participant's diagnostic code and therapist using AHLTA afterward.
- Before the participant's next PT appointment, the participant will complete the baseline questionnaire battery, a 139 question survey battery. The participant may complete the battery immediately on paper, or at a later date online using a link to REDCap that will be sent via encrypted email. This battery must be completed before their next appointment.
- Participants will receive standard PT care as prescribed and scheduled by their therapist. Participation in the study will not alter their care plan.
- Participants will complete follow up questionnaire batteries after their 4th PT appointment\*, 6mo and 12mo post enrollment. The first follow-up questionnaire is a 77 question survey battery. The second and third follow-up points use a 68 question battery. All follow-up questionnaires will be completed remotely via REDCap.
- We will collect de-identified SOAP notes from randomly selected participants and review them for verbiage indicating that the therapist employed principles of PiPT. We will collect up to 30 SOAP notes, pertaining to various physical therapists and throughout various stages of treatment.

##### PT Training

Following the completion of Phase I recruitment, PT staff will be trained in PiPT by the NYU personnel. NYU personnel intend to deliver the training in person; however, they are prepared to deliver virtual, real-time training should COVID protocols make face-to-face training unfeasible.

- PT staff will receive a knowledge quiz at the end of their training sessions to document successful completion of training. PT staff must obtain a passing score (85% or above) on this quiz to be considered proficient.
- We will also assess the PT staff's confidence in implementing PiPT using a seven point Likert scale self-rating derived from a previous study.
- Furthermore, staff will be evaluated on the accurate identification and management of yellow flags using case studies.
- Once the staff shows proficiency in delivering PiPT, the second study phase will begin. There will likely be some overlap between the follow-up data collection of Phase I and the training period.
- After initial training and as Phase II recruitment begins, staff will receive weekly reinforcement sessions for one month, after which they will receive further reinforcement sessions on a biweekly basis as needed.

During training, PT staff will be asked whether they have had previous experience with PiPT. If so, participants who saw these providers, whether during Phase 1 or 2, will be analyzed for a possible confounding effect.

